Study Design:	
This Phase I/II, open label, multicenter study includes a dose evaluation portion (Pilot phase) in which the safety profile of PLX3397 as a single oral agent will be evaluated, followed by an expansion cohort (Phase II) in which the efficacy and safety of PLX3397 administered at the recommended Phase II dose (RP2D) will be evaluated in patients with unresectable stage III or stage IV KIT-mutated melanoma.
 
The Pilot portion of the study follows a 3+3 design to determine if 1000 mg per day is the appropriate dose for the Phase II portion. Three patients are planned to be dosed initially. If 0 or 1 of 3 patients at the 1000 mg dose level cohort experience a dose-limiting toxicity (DLT), 3 additional patients will be enrolled for a total of 6 patients. If ≥ 2 of 6 patients experience a DLT at the 1000 mg per day dose, the dose will be de-escalated to 800 mg per day. If 0 or 1 of 3 patients at the 800 mg per day dose level cohort experiences a DLT, 3 additional patients will be enrolled for a total of 6 patients. If ≥ 2 of 6 patients experience a DLT at the 800 mg dose, the study will be terminated due to intolerability. Additional patients may be enrolled in a dose cohort based on safety and efficacy observations. The RP2D can be either 1000 mg per day or 800 mg per day based on discussions between the Sponsor and the investigators. The RP2D will be further evaluated in an expansion cohort during the Phase II portion of the study.
 
In the Phase II portion of the study, an analysis of anti-tumor response will be carried out after approximately 13 patients have been treated. If 3 or more responses are seen (complete response (CR) and partial response (PR) based upon Response Evaluation Criteria in Solid Tumors (RECIST) v1.1 or PET imaging), an additional approximately 19 patients will be enrolled and treated.

Number of Patients:	
Approximately 44 patients are planned for enrollment
 
Pilot: Approximately 6-12 patients
 
Phase II: Approximately 32 patients

Study Procedures:	Procedures include medical history, physical examination, vital sign assessment, 12-lead electrocardiography (ECG), clinical laboratory evaluations (serum chemistry, hematology, urinalysis), pregnancy testing, and eastern cooperative oncology group (ECOG)

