Endpoints:	
The endpoints in the Pilot portion of the study include:
 
 • DLTs will define the RP2D (1000 mg per day or 800 mg per day) • Safety endpoints (i.e., AEs, clinical laboratory evaluations, ECGs, physical examinations, and vital sign measurements) • PK analysis • Serum/plasma tumor biomarkers including CSF-1 
The exploratory endpoints in the Pilot portion of the study include:
 
 • IHC and molecular analysis of archival and paired fresh tumor biopsy • PET scan evaluation on Day 1 of Cycle 2 compared to Baseline 
The primary endpoint in the Phase II portion of the study includes:
 
 • Objective response rate (ORR), which is the sum of CR and PR by RECIST v1.1. 
The secondary endpoints in the Phase II portion of the study include:
 
 • Duration of response (DoR) • Progression free survival (PFS) • Overall survival (OS) • Safety endpoints (i.e., AEs, clinical laboratory evaluations, ECGs, physical examinations, and vital sign measurements) 
The exploratory endpoints in the Phase II portion of the study include :
 
 • IHC and molecular analysis of archival and paired fresh tumor biopsy • Serum/plasma tumor biomarkers including CSF-1. • ctDNA • PET scan evaluation on Day 1 of Cycle 2 compared to Baseline
Statistical Considerations	The Phase II portion of the study will follow a Simon two-stage design to compare a null ORR of 15% with an alternative ORR of 40% with 90% power and a one-sided type I error of 5%. With the assumption of 10% drop-out, the total sample size will be 32 patients to achieve 29 evaluable patients. Thirteen patients will be enrolled in the first stage, with at least three responses required to proceed to the second stage. Eight responses among 29 evaluable patients are required for PLX3397 to be considered promising.

Table 2-1: Schedule of Events for Pilot Portion of Study

Procedure	Screening	Cycle 1				Cycle 2				Cycle 3 and Subsequent Cycles ²	Extension phase ²¹ (every 28 days)	End of Study ³	Post-Study Follow-up ⁴
	Day -28 to -1 ¹	Day 1	Day 8 ± 3d	Day 15 ± 3d	Day 22 ± 3d	Day 1 ± 3d	Day 8 ± 3d ¹⁷	Day 15 ± 3d	Day 22 ± 3d ¹⁷	Day 1 ± 3d	Day 1 ± 3d		
Consent	X												
Medical history	X												
Archival Tissue ¹⁵	X												
KIT mutation documentation ⁵	X												

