5.0 STUDY DESIGN

5.1. Overview of Study Design

This Phase I/II, open label, multicenter study includes a dose evaluation portion (Pilot phase) in which the safety profile of PLX3397 as a single oral agent will be evaluated, followed by an expansion cohort (Phase II) in which the efficacy and safety of PLX3397 administered at the RP2D will be evaluated in patients with unresectable stage III or stage IV KIT-mutated melanoma (comprising mainly acral, mucosal or CSD forms of the disease).

The Pilot portion of the study follows a 3+3 design to determine if 1000 mg per day is an appropriate dose for the Phase II portion. Three patients are planned to be dosed initially. If 0 or

1 of 3 patients at the 1000 mg dose level cohort experience dose-limiting toxicity (DLT), 3 additional patients will be enrolled for a total of 6 patients. If ≥ 2 of 6 patients experience DLT at the 1000 mg dose, the dose will be de-escalated to 800 mg per day. If 0 or 1 of 3 patients at the 800 mg dose level cohort experiences DLT, 3 additional patients will be enrolled for a total of 6 patients. If ≥ 2 of 6 patients experience DLT at the 800 mg dose, the study will be terminated due to intolerability. Additional patients may be enrolled in a dose cohort based on safety and efficacy observations. The RP2D can be either 1000 mg per day or 800 mg per day based on discussions between the Sponsor and the investigators. The RP2D will be further evaluated in an expansion cohort during the Phase II portion of the study.

In the Phase II portion of the study, an analysis of anti-tumor response will be carried out after approximately 13 patients have been treated. If 3 or more responses (23%) are seen (complete response (CR) and partial response (PR) based upon Response Evaluation Criteria in Solid Tumors (RECIST) v1.1 or PET imaging), an additional approximately 19 patients will be enrolled and treated.

As of June 30 2018, 6 patients were enrolled in the Pilot portion of the study and received 1000 mg per day dose. Two subjects are currently ongoing. Following a preliminary safety and efficacy assessment of these 6 patients, the sponsor decided to discontinue this study. The sponsor informed the 2 remaining subjects of study discontinuation and re-consented the subjects to continue in the extension part of the study.

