11.0 STATISTICAL AND QUANTITATIVE ANALYSES

11.1. Determination of Sample Size

The Pilot portion of this study will determine if 1000 mg PLX3397 is an appropriate dose for the Phase II portion of the study. Traditional 3+3 design will be utilized to determine RP2D.

Eligible patients will enter the study in sets of three. Dose-limiting toxicity (DLT) is defined in Section 7.4. If 0 or 1 of 3 patients at the 1000 mg dose level cohort experience DLT, 3 additional patients will be enrolled for a total of 6 patients. If ≥ 2 of 6 patients experience DLT at the 1000 mg dose, the dose will be de-escalated to 800 mg per day. If 0 or 1 of 3 patients at the 800 mg dose level cohort experiences DLT, 3 additional patients will be enrolled for a total of 6 patients. If ≥ 2 of 6 patients experience DLT at the 800 mg dose, the study will be terminated due to intolerability. Each cohort of patients will be observed for toxicity for 28 days in order to allow time to identify all acute effects of PLX3397. Between 6 and 12 patients will be accrued for the Pilot portion of this study.

The primary objective of the Phase II portion of this study is to evaluate the objective response rate (ORR) at the RP2D. The RP2D will be either the MTD or the alternate dose level below the MTD determined by sponsor and investigator. A true response rate of 40% or more will be considered promising while 15% or lower will not be considered as evidence of activity.

A Simon two-stage design with 90% targeted power and one-sided type I error of 5% will be employed for this study. With the assumption of 10% drop-out, the total sample size will be 32 patients to achieve 29 evaluable patients. During stage one, 13 evaluable patients will be enrolled. If there are 3 or more responses (CR+PR) observed, then the study will continue to the second stage of accrual, and 16 evaluable patients will be enrolled in the second stage. If there are 8 or more responses observed among 29 evaluable patients, the treatment will be considered promising.

With this design, the probability of terminating the study after 13 patients is 69% if the true response rate is 15%. The probability that the treatment will be considered promising is 5%, if the true response rate is 15%, and 90.7% if the true response rate is 40%. Allowing for a 10% unevaluability rate, the overall accrual goal will be 32 patients for the Phase II portion of this study.

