11.7. Efficacy Analysis

The Phase II portion of the study will follow a Simon two-stage design to compare a null ORR of 15% with an alternative ORR of 40% with 90% power and a one-sided type I error of 5%. The total sample size will be 29 evaluable patients. Thirteen patients will be enrolled in the first stage, with at least three responses required to proceed to the second stage. Eight responses among 29 patients are required for PLX3397 to be considered promising. See Section 11.10 for discussion of interim analysis.

Object tumor response to treatment will be evaluated using investigator-determined RECIST v1.1 ([ATTACHMENT 3](#)). PFS, OS and duration of response will be evaluated as secondary efficacy endpoints. PFS will be calculated for each patient as the number of days from study

enrollment to the date of the first documented disease progression or date of death from any cause, whichever occurs first. Overall survival is defined as the time from study enrollment to death from any cause, censoring at the date of last contact or the end of the study. Duration of response (DoR) is defined as the time from the first documentation of objective tumor response (CR or PR) that is subsequently confirmed to the first documentation of disease progression or to death due to any cause, whichever occurs first. DoR will only be calculated for the subgroup of patients with a confirmed objective tumor response. Sponsor may request imaging data for the confirmation of the tumor response.

The Kaplan-Meier method will be used to estimate the median PFS, OS and DoR.

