11.10. Interim Analysis

The Phase II portion of the study will follow a Simon two-stage design to compare a null ORR of 15% with an alternative ORR of 40% with 90% power and a one-sided type I error of 5%. The total sample size will be 29 evaluable patients. Thirteen patients will be enrolled in the first stage before triggering an interim analysis. At least three responses are required to proceed to the second stage. Eight responses among 29 patients are required for PLX3397 to be considered promising.

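### The stage-1 go rule counts RECIST or PET responses in the two design overviews but omits PET in the statistical sections, and the stated 69% early-stop probability is exact only for a RECIST-only count

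*Combined protocol and SAP*

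**What the plan says.** Two places admit PET to the stage-1 count. Section 5.1 says that, after approximately 13 treated patients, three or more CR or PR open stage 2, "based upon Response Evaluation Criteria in Solid Tumors (RECIST) v1.1 or PET imaging), an additional approximately 19 patients will be enrolled and treated". The Study Design row of the synopsis repeats this: "RECIST) v1.1 or PET imaging), an additional approximately 19 patients will be enrolled and treated".

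The other statements of the rule do not mention PET:

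- Synopsis, Statistical Considerations: "Thirteen patients will be enrolled in the first stage, with at least three responses required to proceed to the second stage". Sections 3.2 and 11.7 give the same threshold.
- Section 11.1: "During stage one, 13 evaluable patients will be enrolled", and "If there are 3 or more responses (CR+PR) observed, then the study will continue to the second stage of accrual".
- Section 11.10: "At least three responses are required to proceed to the second stage".

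On the endpoint, the synopsis and Section 10.2 define ORR as CR plus PR by RECIST v1.1, and Section 11.7 states: "Object tumor response to treatment will be evaluated using investigator-determined RECIST v1.1".

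On operating characteristics, Section 11.1 says "the probability of terminating the study after 13 patients is 69% if the true response rate is 15" per cent. It adds a 5% chance of a promising result at that rate and 90.7% at a true rate of 40%.

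On PET itself, Section 4.3 makes tumor response by PET at Cycle 2 Day 1 an exploratory objective. Table 2-2 (footnote 15) schedules the dedicated scan at baseline and Cycle 2 Day 1 for the first 13 Phase II patients. Footnote 12 and Section 9.2.11 allow PET/CT at the scheduled CT assessments. Attachment 3 gives PET supporting roles only: presence or disappearance of bone lesions, detection of new lesions, and upgrade of a residual abnormality to CR. It also cautions that response assessment by FDG-PET needs further study.

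**The concern.** A Simon design has its stated error rates only if the event counted at the interim look is the event used to calculate them. A gate that accepts RECIST or PET responses is looser than one that accepts RECIST responses alone, because every RECIST responder still counts and PET-only responders are added. The dedicated PET scans are scheduled in the same 13 patients whom the gate counts, so the PET reading is a practical possibility.

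Futility stopping is what is at stake. The gate exists to limit enrolment to an inactive treatment, and under the looser rule the stated 69% chance of stopping early is no longer assured. The rule also cannot be applied as written, because nothing says what change on PET would be a partial response.

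**Working it through.** **Inputs (Section 11.1).** Stage 1 has 13 evaluable patients and stops at 2 or fewer responses. Stage 2 adds 16, for a total of 29. Eight or more responses are promising. The null rate is 15% and the alternative 40%.

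**Step 1: reproduce the plan's figures with one response definition in both stages.**

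Early stop = P(X ≤ 2), X ~ Bin(13, 0.15) = 0.1209 + 0.2774 + 0.2937 = 0.692. The plan states 69%.

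P(promising) = Σ over x = 3 to 13 of P(X = x) × P(Y ≥ 8 − x), with Y ~ Bin(16, p).

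- At p = 0.15 this is 0.04999. The plan states 5%.
- At p = 0.40 this is 0.907. The plan states 90.7%.

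Expected sample size at p = 0.15 is 13 + 16 × (1 − 0.692) = 17.9.

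The figures in Section 11.1 are therefore correct for a single response rate applied to both stages.

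**Step 2: direction under the RECIST-or-PET gate.** Let p be the RECIST response rate and d the probability of a response on PET but not on RECIST. A patient passes the gate with probability p + d ≥ p. With 13 patients, P(X ≤ 2) falls as that probability rises. So 0.692 is the maximum, reached only when d = 0. This step needs no assumed value of d.

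**Step 3: size.** The documents give no PET-only rate, so d is an assumption shown over a range. Stage 1 is trinomial (RECIST responder, PET-only responder, neither). The gate opens when the first two categories total at least 3. The final 8-of-29 count uses RECIST responders only.

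| Assumed PET-only rate d | Early stop, p = 15% | Gate opens with fewer than 3 RECIST responses, p = 15% | Expected N, p = 15% | Type I error | Power, p = 40% |
|---|---|---|---|---|---|
| 0% | 69.2% | 0% | 17.9 | 5.0% | 90.7% |
| 1% | 65.4% | 3.8% | 18.5 | 5.1% | 91.2% |
| 2% | 61.5% | 7.7% | 19.2 | 5.2% | 91.7% |
| 5% | 50.2% | 19.0% | 21.0 | 5.4% | 92.7% |
| 10% | 33.3% | 35.9% | 23.7 | 5.6% | 93.7% |

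**Step 4: ceilings.** With no gate at all, P(Bin(29, p) ≥ 8) is 5.86% at p = 0.15 and 94.3% at p = 0.40. No gate of this kind can exceed these values while the final count is RECIST-only.

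**Step 5: sensitivity to the final count.** If stage-1 PET-only responders were also carried into the count of eight, type I error would be 10.5% at d = 5% and 18.2% at d = 10%. Sections 10.2 and 11.7 do not support that reading.

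**The case against.** The strongest reply is that the intended rule can be inferred. The endpoint and the efficacy analysis are RECIST v1.1, PET is exploratory, the stated probabilities match a single definition, and no PET criterion exists to count by. On that view the PET wording is stray text in two overview paragraphs. The inference is reasonable, but it does not remove the conflict: the sections that omit PET are silent on it and do not exclude it by name.

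A related reading is that PET imaging means PET/CT read by RECIST. The words would then be redundant and 69% would hold. However, the text joins the two with *or*, which presents PET as an alternative, and no other section narrows it.

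The upper bound also depends on exactly 13 patients being counted, whereas the two overviews say approximately 13 treated. With no PET-only responders, the early-stop probability at 15% is 73.6% with 12 patients and 64.8% with 14. With 12 patients and a 1% PET-only rate it is 70.1%. This condition stands and should be stated. It does not rescue the 69%, which Section 11.1 itself gives for 13 patients.

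Finally, the size of the effect rests wholly on an assumed PET-only rate, and the study was discontinued before Phase II. Both points are right, and they are why the severity is minor.

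**Conclusion.** The concern holds, at minor severity. The current protocol text contains two stage-1 go rules. The stated 69% is exact for a RECIST-only count and, with 13 patients counted, only an upper bound if PET responses are admitted.

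The direction follows from reading *or* as the union of RECIST and PET responders. The fall to between 65% and 33% is illustrative and depends on the assumed PET-only rates of 1% to 10%.

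The final conclusion is little affected provided the count of eight in 29 is RECIST-only: the type I error excess is at most about 0.9 percentage points (5.86% against 5.0%), and power does not fall. Section 5.1 records that the sponsor discontinued the study after six Pilot patients, so this is a correction to retained Phase II design text.

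**What to change.** In the Study Design row of the synopsis and in Section 5.1, remove PET imaging from the stage-1 rule. State there that the count is CR plus PR by RECIST v1.1 among the 13 evaluable patients of Section 11.1, on the same response definition as the final count. Leave PET as an exploratory endpoint. Section 11.1's figures then apply without change.

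If a PET-based gate is wanted, define a PET response, put the same rule in the synopsis statistical paragraph and in Sections 3.2, 11.1, 11.7 and 11.10, and restate the early-stop probability, type I error and power for that gate.

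The preferred change is wording in two places, with two costs:

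- **Timing.** A go decision could no longer be reached on the week-4 PET. It would wait for the CT at the end of Cycle 2 (week 8) at the earliest, and longer if the count requires confirmed responses, as Attachment 3 indicates for a non-randomised trial with response as primary endpoint. A stop decision needs the CT results under either rule.
- **Power.** The small gain from the looser gate is given up: 0.5 to 3.0 points at assumed PET-only rates of 1% to 10% (91.2% − 90.7% to 93.7% − 90.7%). Power returns to the stated 90.7%.

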5.2. Number of Subjects

Up to approximately 44 patients are planned for enrollment.

Pilot Portion: Approximately 6-12 patients

Phase II: Approximately 32 patients

5.3. Duration of Study

Screening Period:

The Screening period will be 28 days prior to the first dosing for each patient.

Treatment Period:

Subjects will receive study drug twice daily during each 28-day cycle. There is no limit to the number of treatment cycles that can be administered. The treatment will continue until disease progression, unacceptable toxicity, consent withdrawal, or a protocol violation.

Those subjects deriving clinical benefit from therapy defined as stable disease or better at the cut-off date, will be offered the opportunity to continue therapy with pexidartinib in the extension phase of this protocol until disease progression, unacceptable toxicity, consent withdrawal, or a protocol violation.

Follow-up Period:

All patients will undergo an End-of-Study evaluation within 28 days of the last dose of study drug and prior to the initiation of any new anti-cancer therapy (if applicable [see Section 8.4]). Thereafter, patients will be contacted by phone every 3 months during year 1 and every 6 months thereafter to obtain information about subsequent treatment(s) and survival status.

6.0 STUDY POPULATION

Patients must meet the inclusion and exclusion criteria to be enrolled in the study, unless a planned protocol deviation is granted by the Sponsor.

6.1. Inclusion Criteria

Each patient must meet all of the following inclusion criteria to be enrolled in the study to treatment:

1. Age ≥ 18 years
2. Unresectable stage III or stage IV melanoma which is histologically confirmed at the treating institution with KIT mutation(s) not known to be resistant to PLX3397.

Note: Patients with KIT exon 8, 9, 11, 13, and 14 mutations are the most likely to be sensitive to PLX3397. Patients with KIT exon 17 or 18 mutations D816V, Y823D, and A829P should not be enrolled as they are not sensitive to PLX3397. Other KIT exon 17 or 18 mutations may be sensitive to PLX3397 and should be enrolled.

3. No limit on prior systemic therapies for melanoma. Patients who have not received prior therapy are eligible if they have a potentially sensitive KIT mutation.
4. Presence of measurable lesions by RECIST v1.1
5. Eastern cooperative oncology group (ECOG) performance status 0, 1, or 2
6. Life expectancy ≥ 3 months in the judgment of the investigator
7. Adequate organ and bone marrow function
 - a. Absolute neutrophil count (ANC) $\geq 1.5 \times 10^9/L$, Hgb ≥ 10 g/dL, platelet count $\geq 100 \times 10^9/L$
 - b. AST/ALT $\leq 2.5 \times$ upper limit of normal (ULN) or $< 5 \times$ ULN in the presence of liver metastases, total bilirubin ≤ 1.5 ULN (unless due to Gilbert's Syndrome, in which case it must be ≤ 2.5 mg/dL), albumin ≥ 3.0 g/dL
 - c. Serum creatinine $\leq 1.5 \times$ ULN or calculated creatinine clearance (CrCl) > 60 mL/min using the Cockcroft-Gault formula

Patients may be transfused or receive granulocyte-colony stimulating factor (G-CSF) or growth factors.

8. Women of child-bearing potential must have a negative serum pregnancy test at Screening and must agree to use an effective form of contraception from the time of the negative pregnancy test up to 3 months after the last dose of study drug. Effective forms of contraception include abstinence, hormonal contraceptive (injectable or implantable) in conjunction with a barrier method, or a double barrier method. Women of non-child-bearing potential must have been postmenopausal for ≥ 1 year or surgically sterile.
9. Fertile men must agree to use an effective method of birth control during the study and for up to 3 months after the last dose of study drug.
10. Willingness and ability to provide written informed consent prior to any study-related procedures and to comply with all study requirements

